#### **Appendix 8 - Enrollment Medication Dosing Recommendations**

#### A1c <5.7

- 1. Not taking medications→ Does not have diabetes. Retest in A1c in 1 year
- Nonadherent with medications → May not have diabetes or may have diet-controlled diabetes. Stop
  medications and retest A1c in 3 months
- 3. Taking metformin without problems
  - a. Metformin 500-1000 mg  $\rightarrow$  metformin 850 mg
  - b. Metformin 1500-2550 mg  $\rightarrow$  metformin 1700 mg
- 4. Taking metformin with problems
  - a. Metformin 500-850 mg, refuses to take metformin → Stop medications, retest in 3 months
  - b. Metformin 500-850 mg, agrees to take metformin  $\rightarrow$  metformin 850 mg
  - c. Metformin 1000-1700 mg  $\rightarrow$  metformin 850 mg

<sup>17 See Appendix 6 for further details of risk assessment in patients with chest pain

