### 2.3 Study Agent

In this study, we will be using a smartphone application that we developed to guide CHWs through the clinical assessment of patients with diabetes including collection of demographic data and past medical history, assessment of medication history, adherence, and adverse effects, measurement of glycemic control, screening for complications, medication administration and titration, and patient counseling. The application uses the CommCare platform by Dimagi and will be run on password-protected and encrypted Android smartphones. This application is based on web forms, which allow for skip logic questions and algorithmic processing of data. The application can be used offline. When internet access is available, collected data is uploaded to a secure server. The specific protocols and algorithms programmed into this application are described in further detail in the relevant sections of this protocol and its appendices.

We will use the following medications in our study (all FDA approved and being used for approved indications):

- Metformin HCI regular-release tablets 850 mg
  - Description: Oral biguanide antidiabetic medication. First line medication for type 2 diabetes and used as monotherapy or in combination with other medications. Low risk of lactic acidosis

Version #: 1.0

Deleted: consists of Enketo

Deleted: utilize Excel-based programing to

Deleted: These forms run in a smartphone browser and

**Deleted:** In our case, we are using password-protected Android smartphones with the Google Chrome mobile browser.

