## 6.4 Route of Administration

All medications are administered by mouth. Patients will be treated with at least one of the three medications during the entire duration of the study and their participation in the diabetes treatment program (so, at least 6 months), aside from patients who may be observed off of medication to see if their diabetes is diet-controlled. Whether a patient is taking one of these medications or not depends on their individual characteristics, including glycemic control and targets, experience of side effects, and medication adherence, as described by the treatment protocols outlined below and in the appendices.

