# 7 Study Procedures

# 7.1LABS

All patients will have POC HbA1c testing performed at baseline and every 3 months. The ADA does recommend individualization of A1c testing, advising quarterly checks in patients not meeting glycemic goals and at least twice yearly in those meeting treatment goals. While we do intend to implement individualized testing in the diabetes program after the study period, testing will be every 3 months for all patients during the study period to allow for more uniform evaluation of program efficacy at the predetermined times of endpoint analysis (6 and 12 months for primary endpoints).

A1c testing will be performed with A1CNow®+ (PTS Diagnostics) POC capillary blood analyzers. This analyzer has been granted a CLIA waiver and has been certified by the National Glycohemoglobin Standardization Program (NGSP).

Capillary blood glucose measurements will be conducted at baseline and monthly using the Bayer Contour® POC system. This is also CLIA-waived and has been validated in comparisons with plasma/serum glucose analyzers.

Both aforementioned POC testing systems are designed to be used by laypeople and patients without medical training, making them very appropriate for use by frontline health workers, as in our study.

Testing of serum creatinine will be checked at baseline for all patients with prior history of chronic kidney disease prior to administration of metformin or glibenclamide. Baseline creatinine will also be strongly recommended for patients with hypertension (defined as either taking antihypertensives or baseline BP  $\geq$ 140/90) and/or duration since diagnosis of diabetes of 10 years or more. Serum creatinine will be checked at SLMH and reviewed by the medical director, who will then determine patient eligibility for metformin and/or glibenclamide therapy based on calculated eGFR.

Ideally, serum creatinine would be tested in all patients at baseline and prior to administration of metformin and glibenclamide. However, this is not performed routinely for diabetic patients in the San Lucas area due to the expense and availability of travel. Requiring testing for all patients prior to administration would likely severely restrict participation as it is likely many patients would not travel to San Lucas to have necessary testing done and subsequently be lost to follow up. For this reason, we have adopted a risk-factor based targeted testing strategy for checking renal function.

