#### 7.4.2 Follow up:

Acceptable Window for Study Visits (including weekends)

Visit	Window	Activities
Monthly follow up visits	+/- 1 week	Assessment of the following:         Outright Medication adherence and tolerance         Glycemic control with blood glucose         Oresence of diabetes complications         Refill of medications, with titration of dosage as needed         Diabetic education
Month 3 visit	+/- 1 week	Same as for monthly visit with the exception that A1c is checked (if indicated) in addition to blood glucose and is used for medication titration

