### Monthly Visits

CHWs will meet with patients once per month to follow up on adherence and tolerance to medications, assess glycemic control, assess for complications of diabetes, refill medications (with dosing adjustments as needed for side effects, non-adherence or poor glycemic control), and provide diabetic education. These monthly visits will be facilitated by the smartphone application monthly protocol. This protocol mirrors the enrollment protocol as described above, with the following exceptions:

- Basic demographic information and medical history are not reassessed. This information is carried forward from the enrollment visit
- Blood glucose alone is collected. A1c is not collected unless it was recommended to be done the month
  prior and was not collected at that time
- Algorithms for medication adjustments are based on blood glucose, preferencing fasting glucose over postprandial glucose (Appendix 10)

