### Month 3 Visit

Version #: 1.0

[name]

At every 3rd monthly visit, starting with the visit 3 months after enrollment, A1c will be assessed. When A1c is checked, the month 3 medication titration algorithm (Appendix 11), is used rather than the monthly titration algorithm, which uses blood glucose. This protocol also considers the current glucose measurement to account for cases in which glycemic control may have improved significantly in the past month due to medication or lifestyle changes, but A1c may still be above goal due to earlier hyperglycemia. For example, if a patient with A1c goal of 7 has an A1c of 7.5, but FBG of 105, the application will recommend that the patient continues with the current medication dosing rather than recommending a dose increase. Other than checking A1c and using the A1c-based algorithm as indicated, the procedures performed at the month 3 visit are identical to those of the monthly visit.

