#### 5.7≤ A1c <6.5

- 1. Not taking medications → Patient has prediabetes. Counsel on diet and exercise and retest yearly
- 2. Nonadherent with medications  $\rightarrow$  May have diabetes. Stop medications and recheck A1c in 3 months
- 3. Taking metformin without problems
  - a. Metformin 500-1000 mg  $\rightarrow$  metformin 850 mg
  - b. Metformin 1500-2550 mg  $\rightarrow$  metformin 1700 mg
- 4. Taking metformin with problems
  - a. Metformin 500-850 mg, refuses to take metformin  $\rightarrow$  Stop medications, retest A1c in 3 months
  - b. Metformin 500-850 mg, agrees to take metformin  $\rightarrow$  metformin 850 mg
  - c. Metformin 1000-1700 mg  $\rightarrow$  metformin 850 mg
  - d. Metformin 2000-2550 mg → metformin 1700 mg
- 5. Taking glibenclamide, with or without hypoglycemia or hypoglycemia symptoms
  - a. All doses → metformin 1700 mg
- 6. Taking glibenclamide, previous problems with metformin, with or without hypoglycemia or hypoglycemia symptoms
  - a. All doses, agrees to take metformin  $\rightarrow$  metformin 850 mg
  - b. All doses, refuses to take metformin  $\rightarrow$  stop medications, recheck A1c in 3 months
- 7. Taking metformin and glibenclamide, with or without hypoglycemia or hypoglycemia symptoms
  - a. Metformin 500-1000 mg + glibenclamide any dose  $\rightarrow$  metformin 850 mg
  - b. Metformin 1500-2550 mg + glibenclamide any dose  $\rightarrow$  metformin 1700 mg

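### Appendix 8 sets a yearly A1c retest for unmedicated enrollees with A1c below 6.5%, against the 3-monthly testing in section 7.1; any who stay enrolled could lack a 6-month A1c

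*Combined protocol and SAP*

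**What the plan says.** Appendix 8 (Enrollment Medication Dosing Recommendations) has two entries for enrollees who are not taking medication and whose A1c is below 6.5%. In the band below 5.7% the instruction is "Does not have diabetes. Retest in A1c in 1 year". In the band from 5.7% to below 6.5% the patient is labelled prediabetic and the instruction is "Counsel on diet and exercise and retest yearly".

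Section 7.1 says that "testing will be every 3 months for all patients during the study period", and defers individualized intervals until after the study so that efficacy is assessed uniformly at the endpoint times. The Month 3 Visit text in section 7.4.2 agrees: "At every 3rd monthly visit, starting with the visit 3 months after enrollment, A1c will be assessed". The overview in section 2.1 sets the same interval.

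Section 2.3 ties the appendices to the application: "The specific protocols and algorithms programmed into this application are described in further detail in the relevant sections of this protocol and its appendices". The visit table in section 7.4.2 describes the month 3 visit as a monthly visit "with the exception that A1c is checked (if indicated) in addition to blood glucose".

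Section 9.2.2.1 restricts each time-point analysis to patients followed to that time point. Section 8.3 analyzes all enrolled patients to the extent of their participation and plans a subgroup at or below goal at baseline.

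**The concern.** The two intervals cannot both hold for the same patient. A patient kept to the Appendix 8 interval has no A1c at months 3, 6 or 9; the next one falls at month 12. Month 6 is the only primary time point that the plan guarantees, because follow-up to 12 months depends on funding and logistics (sections 4.1 and 7.4.4).

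Without a 6-month value a patient cannot enter the paired t test or the McNemar table. The loss would not be random: it would fall on patients chosen by a low baseline value of the outcome itself. They are at goal already and have little room to improve, so losing them makes the average improvement look larger. That is the kind of non-uniform evaluation section 7.1 says it wants to avoid.

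**Working it through.** **Can such patients be in the study?** Eligibility rests on a prior diagnosis, with no A1c floor (section 5.2). Low A1c is not an exclusion (5.3), an exit criterion (2.7.2) or a listed reason for withdrawal (5.7.2). The enrollment-visit text in 7.4.1 itself gives the example of an unmedicated patient with an A1c of 5.2. In the same two Appendix 8 bands, every entry that stops a drug sets a 3-month recheck. Only the two entries for patients on no medication depart from the 3-month cycle.

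**The plan's own power figure.** Inputs from section 8.1: SD 2.4, within-subject correlation 0.928, n = 100, alpha 0.05 (two-sided, from 8.2), power 80%.

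- SD of the change = 2.4 × √(2 × (1 − 0.928)) = 0.911.
- Detectable change at n = 100 = 0.2577 with t quantiles (0.255 with normal quantiles), against 0.257 stated. The figure reproduces.

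**How many patients?** The documents do not say, so this step is assumption. Section 2.1 reports 13% with good control and 58% taking medication regularly. I take A1c as normal with SD 2.4, read the 13% as A1c ≤7 or as A1c ≤8, and take 42% (the complement of 58%) or half of that, 21%, as unmedicated, independently of A1c.

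- 13% at ≤7: mean = 7 + 1.126 × 2.4 = 9.70; P(A1c <6.5) = 0.0910.
- 13% at ≤8: mean = 8 + 1.126 × 2.4 = 10.70; P(A1c <6.5) = 0.0399.

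Multiplying by 0.42 or 0.21 gives the fraction f affected. If these patients are lost and would not have changed, a true mean fall of 1.00 reads 1/(1 − f), and the plan's at-goal gain of 30.2 − 13 = 17.2 points reads 17.2/(1 − f). The last column divides by the 13 per 100 at goal at baseline.

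| 13% read as | Unmedicated | Affected per 100 | Fall of 1.00 reads | Gain of 17.2 reads | Share of at-goal subgroup |
|---|---|---|---|---|---|
| ≤7 | 42% | 3.82 | 1.040 | 17.88 | 29.4% |
| ≤7 | 21% | 1.91 | 1.019 | 17.54 | 14.7% |
| ≤8 | 42% | 1.68 | 1.017 | 17.49 | 12.9% |
| ≤8 | 21% | 0.84 | 1.008 | 17.35 | 6.5% |

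**Effect on precision and tests.** The detectable change is 0.258 at n = 100, 0.259 at n = 99 and 0.263 at n = 96. Patients at goal at both times are concordant pairs, so the McNemar statistic does not depend on them; only the reported percentages move. The baseline at-goal share would read (13 − 0.84)/(100 − 0.84) = 12.3% to (13 − 3.82)/(100 − 3.82) = 9.5%, instead of 13%. The above-goal and A1c ≥9 subgroups are untouched.

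**The case against.** The strongest reply is that section 7.1 governs. Sections 2.1, 7.1 and 7.4.2 all set 3-monthly A1c, so a missed test would be a deviation from a clear rule. The medical director also reviews every visit within a week and may withdraw a patient at clinical discretion. On this view the yearly advice is addressed to people the program will not treat. Much of this stands. The documents do not say whether someone labelled as not having diabetes stays in the study, and nothing says that the Appendix 8 text switches off the 3-monthly test. So a miss is possible, not established. What remains is that the tool the CHW follows carries an interval the body of the protocol rules out, and no text tells the reviewing physician to restore the shorter one.

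A reader might infer more from four other places, and the documents do not support it:

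- The Monthly Visits text says "A1c is not collected unless it was recommended to be done the month". The sentence goes on to cover an A1c that was due the month before and not done. It is a catch-up rule and protects the endpoint.
- Section 6.4 says patients receive at least one drug throughout, "aside from patients who may be observed off of medication to see if their diabetes is diet-controlled". That exception best matches the Appendix 8 entries that stop drugs and recheck in 3 months, not the yearly entries.
- Appendices 10 and 11 have no dosing entry for a patient on no drug. That leaves titration undefined; it does not stop A1c from being measured.
- The conditional wording in the visit table need not make A1c optional. Appendix 10 speaks of checking A1c when next indicated, apparently meaning when next due.

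**Conclusion.** The contradiction is real and worth correcting, but minor. It concerns only enrollees on no medication with A1c below 6.5% who remain in the study. If the application's interval were followed, they would have no A1c for the 6-month primary analysis or for the 3- and 9-month secondary ones; a 1-year retest could still supply the 12-month value.

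The size is about 1 to 4 per 100 enrolled, and it rests on the assumptions above. The 42% is probably too high, because patients who take medication irregularly go to a different entry with a 3-month retest. The 21% has no source in the documents. If treatment and A1c are not independent, the number could lie outside the range in either direction. Within the range, neither the main result nor the power moves enough to change a conclusion of this pilot. The subgroup at or below goal at baseline could lose about 6% to 29% of its members, so it is where the matter would show.

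A reader might go further and conclude that the plan will lose these patients, or that the primary result is biased. The documents support only that the conflicting instruction makes such a loss possible.

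**What to change.** 1. State in both Appendix 8 entries that the yearly interval applies only after the study period.
2. Have the application prompt A1c at months 3, 6, 9 and, if followed, 12 for every patient still enrolled, including those on no medication.
3. Remove the conditional words from the month 3 row of the visit table, so that it matches section 7.1.
4. Report the 6-month result with and without patients whose diabetes was not confirmed at enrollment. Whether they belong in the main efficacy estimate is partly a choice of target population, and showing both leaves it open to the reader.

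The cost is one sentence, one prompt, one deletion and one repeat of the 6-month analysis. Compared with following Appendix 8, it means three more tests per affected patient by month 9: 3 × 0.84 = 2.5 to 3 × 3.82 = 11.5 per 100 enrolled under the same assumptions. None goes beyond what section 7.1 already plans. Sample size, endpoints and tests are unchanged. The mean improvement may look slightly smaller once these patients are measured.

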#### [name]

- d. Metformin 2000-2550 mg  $\rightarrow$  metformin 1700 mg
- Taking glibenclamide, with or without hypoglycemia or hypoglycemia symptoms

   All doses → metformin 1700 mg
- a. All doses → metrormin 1700 mg
  b. Taking glibenclamide, previous problems with metformin
  - a. All doses, agree to take metformin  $\rightarrow$  metformin 850 mg
  - a. All doses, agree to take metformin  $\rightarrow$  metformin coording b. All doses, refuses to take metformin  $\rightarrow$  discontinue medications, recheck A1c in 3 months
- Taking glibenclamide with hypoglycemia or hypoglycemia symptoms, previous problems with metformin

   All doses, agrees to take metformin → metformin 850 mg
  - b. All doses, refuses to take metformin  $\rightarrow$  stop medications, recheck A1c in 3 months
- 8. Taking metformin and glibenclamide, with or without hypoglycemia or hypoglycemia symptoms
  - a. Metformin 500-1000 mg + glibenclamide any dose  $\rightarrow$  metformin 850 mg
  - b. Metformin 1500-2550 mg + glibenclamide any dose → metformin 1700 mg
- 9. Taking metformin and glibenclamide, problems with metformin
  - a. Metformin 500-850 mg + glibenclamide any dose, agrees to take metformin → metformin 850 mg
     b. Metformin 500-850 mg + glibenclamide any dose, refuses to take metformin → stop medications, recheck A1c in 3 months
  - c. Metformin 1000-1700 mg + glibenclamide any dose  $\rightarrow$  metformin 850 mg
  - d. Metformin 2000-2550 mg + glibenclamide any dose  $\rightarrow$  metformin 1700 mg
- 10. Taking metformin and glibenclamide, with hypoglycemia or hypoglycemia symptoms, problems with metformin
  - a. Metformin 500-850 mg + glibenclamide any dose, agrees to take metformin  $\rightarrow$  metformin 850 mg
  - b. Metformin 500-850 mg + glibenclamide any dose, refuses to take metformin → stop medications, recheck A1c in 3 months
  - c. Metformin 1000-1700 mg + glibenclamide any dose  $\rightarrow$  metformin 850 mg
  - d. Metformin 2000-2550 mg + glibenclamide any dose  $\rightarrow$  metformin 1700 mg

#### 5.7≤ A1c <6.5

- 1. Not taking medications → Patient has prediabetes. Counsel on diet and exercise and retest yearly
- 2. Nonadherent with medications  $\rightarrow$  May have diabetes. Stop medications and recheck A1c in 3 months
- 3. Taking metformin without problems
  - a. Metformin 500-1000 mg  $\rightarrow$  metformin 850 mg
  - b. Metformin 1500-2550 mg  $\rightarrow$  metformin 1700 mg
- 4. Taking metformin with problems
  - a. Metformin 500-850 mg, refuses to take metformin  $\rightarrow$  Stop medications, retest A1c in 3 months
  - b. Metformin 500-850 mg, agrees to take metformin  $\rightarrow$  metformin 850 mg
  - c. Metformin 1000-1700 mg  $\rightarrow$  metformin 850 mg
  - d. Metformin 2000-2550 mg → metformin 1700 mg
- 5. Taking glibenclamide, with or without hypoglycemia or hypoglycemia symptoms
  - a. All doses → metformin 1700 mg
- 6. Taking glibenclamide, previous problems with metformin, with or without hypoglycemia or hypoglycemia symptoms
  - a. All doses, agrees to take metformin  $\rightarrow$  metformin 850 mg
  - b. All doses, refuses to take metformin  $\rightarrow$  stop medications, recheck A1c in 3 months
- 7. Taking metformin and glibenclamide, with or without hypoglycemia or hypoglycemia symptoms
  - a. Metformin 500-1000 mg + glibenclamide any dose  $\rightarrow$  metformin 850 mg
  - b. Metformin 1500-2550 mg + glibenclamide any dose  $\rightarrow$  metformin 1700 mg

#### [name]

- Taking metformin and glibenclamide, problems with metformin, without hypoglycemia or hypoglycemia symptoms
  - a. Metformin 500-850 mg + glibenclamide any dose, agrees to take metformin → metformin 850 mg
     b. Metformin 500-850 mg + glibenclamide any dose, refuses to take metformin → glibenclamide 2.5 mg
  - c. Metformin 1000-1700 mg + glibenclamide any dose  $\rightarrow$  metformin 850 mg
  - d. Metformin 2000-2550 mg + glibenclamide any dose  $\rightarrow$  metformin 1700 mg
- Taking metformin and glibenclamide, with hypoglycemia or hypoglycemia symptoms, problems with metformin
  - a. Metformin 500-850 mg + glibenclamide any dose, agrees to take metformin  $\rightarrow$  metformin 850 mg
  - b. Metformin 500-850 mg + glibenclamide any dose, refuses to take metformin  $\rightarrow$  stop medications, recheck A1c in 3 months
  - c. Metformin 1000-1700 mg + glibenclamide any dose  $\rightarrow$  metformin 850 mg
  - d. Metformin 2000-2550 mg + glibenclamide any dose  $\rightarrow$  metformin 1700 mg

#### 6.5≤ A1c ≤Tx goal

- Not taking medications or nonadherent, no hypoglycemia or hypoglycemia symptoms, no problems with metformin → metformin 1700 mg
- Not taking medications or nonadherent, no hypoglycemia or hypoglycemia problems, problems with metformin
  - a. Agrees to take metformin  $\rightarrow$  metformin 850 mg
  - b. Refuses to take metformin → glibenclamide 2.5
- 3. Not taking medications or nonadherent, hypoglycemia or hypoglycemia symptoms, problems with metformin
  - a. Agrees to take metformin  $\rightarrow$  metformin 850 mg
  - b. Refuses to take metformin, prescribed glibenclamide >2.5 mg  $\rightarrow$  glibenclamide 2.5 mg
  - e. Refuses to take metformin, prescribed glibenclamide 2.5 mg  $\rightarrow$  MD consult
- 4. Taking metformin without problems
  - a. Metformin 500-1000 mg  $\rightarrow$  metformin 850 mg
  - b. Metformin 1500-2550 mg  $\rightarrow$  metformin 1700 mg
- 5. Taking metformin with problems
  - a. Metformin 500-850 mg, agrees to take metformin  $\rightarrow$  metformin 850 mg
  - b. Metformin 500-850 mg, refuses to take metformin  $\rightarrow$  glibenclamide 2.5 mg
  - c. Metformin 1000-1700 mg  $\rightarrow$  metformin 850 mg
  - d. Metformin 2000-2550 mg  $\rightarrow$  metformin 1700 mg
- 6. Taking glibenclamide without problems
- a. All doses  $\rightarrow$  metformin 1700 mg
- 7. Taking glibenclamide without problems, previous problems with metformin
  - a. Willing to take metformin
    - i. Glibenclamide 2.5 mg  $\rightarrow$  metformin 850 mg
    - ii. Glibenclamide 5 mg  $\rightarrow$  metformin 850 mg + glibenclamide 2.5 mg
    - iii. Glibenclamide 10 mg  $\rightarrow$  metformin 850 mg + glibenclamide 5 mg
    - iv. Glibenclamide 15-20 mg  $\rightarrow$  metformin 850 mg + glibenclamide 10 mg
  - b. Refuses to take metformin
    - i. Glibenclamide 2.5-10 mg → continue current dose of glibenclamide
  - ii. Glibenclamide 15-20 mg  $\rightarrow$  glibenclamide 10 mg
- 8. Taking glibenclamide with hypoglycemia or hypoglycemia symptoms

Version #: 1.0

[name]

- a. All doses  $\rightarrow$  metformin 1700 mg
- 9. Taking glibenclamide with hypoglycemia or hypoglycemia symptoms, previous problems with metformin a. Agrees to take metformin
  - i. Glibenclamide 2.5-5 mg  $\rightarrow$  metformin 850 mg
  - ii. Glibenclamide 10 mg  $\rightarrow$  metformin 850 mg + glibenclamide 2.5 mg
  - iii. Glibenclamide 15 mg  $\rightarrow$  metformin 850 mg + glibenclamide 5 mg
  - iv. Glibenclamide 20 mg  $\rightarrow$  metformin 850 mg + glibenclamide 10 mg
  - b. Refuses to take metformin
    - i. Glibenclamide 2.5 mg  $\rightarrow$  stop medications, recheck A1c in 3 months
    - ii. Glibenclamide 5 mg  $\rightarrow$  glibenclamide 2.5 mg
    - iii. Glibenclamide 10 mg  $\rightarrow$  glibenclamide 5 mg
    - iv. Glibenclamide 15-20 mg  $\rightarrow$  glibenclamide 10 mg
- 10. Taking metformin and glibenclamide without problems
  - a. Metformin 500-1000 mg + glibenclamide 2.5-10 mg → metformin 850 mg + current glibenclamide dose
  - b. Metformin 500-1000 mg + glibenclamide 15-20 mg → metformin 850 mg + glibenclamide 10 mg
  - c. Metformin 1500-2550 mg + glibenclamide 2.5-10 mg  $\rightarrow$  metformin 1700 mg + current glibenclamide dose
  - d. Metformin 1500-2550 mg + glibenclamide 15-20 mg → metformin 1700 mg + glibenclamide 10 mg
- 11. Taking metformin and glibenclamide, problems with metformin
  - a. Metformin 500-850 mg + glibenclamide 2.5-10 mg, agrees to take metformin →metformin 850 mg + current glibenclamide dose
  - b. Metformin 500-850 mg + glibenclamide 15-20 mg, agrees to take metformin →metformin 850 mg
     + glibenclamide 10 mg
  - c. Metformin 500-850 mg + glibenclamide 2.5-10 mg, refuses to take metformin  $\rightarrow$  current alibenclamide dose
  - d. Metformin 500-850 mg + glibenclamide 15-20 mg, refuses to take metformin → glibenclamide 10 mg
  - e. Metformin 1000-1700 mg + glibenclamide 2.5-10 mg  $\rightarrow$  metformin 850 mg + current glibenclamide dose
  - f. Metformin 1000-1700 mg + glibenclamide 15-20 mg  $\rightarrow$  metformin 850 mg + glibenclamide 10 mg
  - g. Metformin 2000-2550 mg + glibenclamide 2.5-10 mg  $\rightarrow$  metformin 1700 mg + current glibenclamide dose
  - h. Metformin 2000-2550 mg + glibenclamide 15-20 mg → metformin 1700 mg + glibenclamide 10 mg

12. Taking metformin and glibenclamide with hypoglycemia or hypoglycemia symptoms

- a. Metformin 500-1000 mg + glibenclamide 2.5 mg  $\rightarrow$  metformin 850 mg
- b. Metformin 500-1000 mg + glibenclamide 5 mg  $\rightarrow$  metformin 850 mg + glibenclamide 2.5 mg
- c. Metformin 500-1000 mg + glibenclamide 10 mg  $\rightarrow$  metformin 850 mg + glibenclamide 5 mg
- d. Metformin 500-1000 mg + glibenclamide 15-20 mg  $\rightarrow$  metformin 850 mg + glibenclamide 10 mg
- e. Metformin 1500-2000 mg + glibenclamide 2.5 mg  $\rightarrow$  metformin 1700 mg
- f. Metformin 1500-2000 mg + glibenclamide 5 mg  $\rightarrow$  metformin 1700 mg + glibenclamide 2.5 mg
- g. Metformin 1500-2000 mg + glibenclamide 10 mg  $\rightarrow$  metformin 1700 mg + glibenclamide 5 mg
- h. Metformin 1500-2000 mg + glibenclamide 15-20 mg  $\rightarrow$  metformin 1700 mg + glibenclamide 10 mg
- i. Metformin 2550 mg + glibenclamide 2.5 mg  $\rightarrow$  metformin 2550 mg

Version #: 1.0

